6.8.1 Secondary Malignancy

A secondary malignancy is a cancer caused by treatment for a previous malignancy (e.g., treatment with investigational agent/intervention, radiation or chemotherapy). A secondary malignancy is not considered a metastasis of the initial neoplasm.

- Three options are available to describe the event:
 - Leukemia secondary to oncology chemotherapy (e.g., acute myelocytic leukemia [AML])
 - Myelodysplastic syndrome (MDS)
 - Treatment-related secondary malignancy

6.8.2 Second Malignancy

A second malignancy is one unrelated to the treatment of a prior malignancy (and is NOT a metastasis from the initial malignancy). Second malignancies require ONLY routine reporting via CDUS unless otherwise specified.

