7 STUDY ASSESSMENTS AND PROCEDURES

7.1 Flow Chart/Time and Events Schedule

Table 7.1-1: Screening Procedural Outline

Procedure	Screening Visit (Day -28 till Day -1 prior to Randomization)	Notes
Eligibility Assessments		
Informed Consent	x	
Inclusion/Exclusion Criteria	x	All inclusion/exclusion criteria should be assessed during screening and confirmed prior to randomization.
Medical History	x	
Review of pathology report	x	
Tumor Tissue Samples	x	Sufficient tumor tissue from the resected site of the disease (a block or a minimum of 15 slides) must be available and sent to Moffitt Cancer Center for biomarker analysis. If biopsy is performed at the treatment sites, fresh tumor will be requested to biomarker studies to establish tumor cell lines.
Safety Assessments		
Physical Examination	x	Including height
Vital Signs	x	Including weight, blood pressure (BP), heart rate (HR), temperature
Oxygen saturation	x	By pulse oximetry
Performance Status (ECOG)	x	Within 14 days prior to randomization
Assessment of Signs and Symptoms	x	Within 14 days prior to randomization
Electrocardiogram (ECG)	x	Within 14 days prior to randomization
Laboratory Tests	x	On site/local complete blood count (CBC) w/differential, Chemistry panel including: LDH, AST, ALT, ALP, T.Bili, amylase, lipase, blood urea nitrogen (BUN) or serum urea level, creatinine, uric acid, Ca, Mg, Na, K, Cl, Glucose, endocrine panel (TSH, Free T4, Free T3), Hep B/C (HBV sAG, HCV RNA), within 14 days prior to randomization.
Pregnancy Test	x	WOCBP only (within 24 hours prior to start). Serum or Urine.
Efficacy assessment		
Surveillance assessments	x	Clinical exam and/or CT scan of the involved disease sites and all known sites of resected disease and brain MRI (brain CT allowable if MRI is contraindicated or if there is no known history of resected brain lesions).
Other		
Randomization	x	

Table 7.1-2: On-Treatment Assessments Week 1 - Week 9

Procedure	Wk1	Wk2	Wk3	Wk5	Wk7	Wk9	Notes
Safety Assessments							
Targeted Physical Examination	x	x	x	x	x	x	To be performed within 72 hours of dosing, or while undergoing radiation therapy as an on treatment visit
Vital Signs	x	x	x	x	x	x	Including BP, HR, temperature
Oxygen saturation	x	x	x	x	x	x	By pulse oximetry prior to dosing
Weight and performance status	x	x	x	x	x	x	Within 72 hours of dosing or while undergoing radiation therapy as an on treatment visit
Adverse Events Assessment	Continuously						See Section 6.8. and Section 8

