8.1 Serious Adverse Events

A Serious Adverse Event (SAE) is any untoward medical occurrence that at any dose:

- results in death
- is life-threatening (defined as an event in which the subject was at risk of death at the time of the event; it does not refer to an event which hypothetically might have caused death if it were more severe)
- requires inpatient hospitalization or causes prolongation of existing hospitalization (see NOTE below)
- results in persistent or significant disability/incapacity
- is a congenital anomaly/birth defect
- is an important medical event (defined as a medical event(s) that may not be immediately life-threatening or result in death or hospitalization but, based upon appropriate medical and scientific judgment, may jeopardize the subject or may require intervention [eg, medical, surgical] to prevent one of the other serious outcomes listed in the definition above.) Examples of such events include, but are not limited to, intensive treatment in an emergency room or at home for allergic bronchospasm; blood dyscrasias or convulsions that do not result in hospitalization.) Potential drug induced liver injury (DILI) is also considered an important medical event. (See Section 6.6 for the definition of potential DILI.) Suspected transmission of an infectious agent (eg, pathogenic or nonpathogenic) via the study drug is an SAE.

Deaths due to disease progression will not be reported as an SAE.

Although pregnancy, overdose, cancer, and potential drug induced liver injury (DILI) are not always serious by regulatory definition, these events must be handled as SAEs.

Any component of a study endpoint that is considered related to study therapy (eg, death is an

endpoint, if death occurred due to anaphylaxis, anaphylaxis must be reported) should be reported as SAE.

NOTE:

The following hospitalizations are not considered SAEs:

- a visit to the emergency room or other hospital department < 24 hours, that does not result in admission (unless considered an important medical or life-threatening event)
- elective surgery, planned prior to signing consent
- admissions as per protocol for a planned medical/surgical procedure
- routine health assessment requiring admission for baseline/trending of health status (eg, routine colonoscopy)
- medical/surgical admission other than to remedy ill health and planned prior to entry into the study. Appropriate documentation is required in these cases

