8.1.1 Serious Adverse Event Collection and Reporting

Sections 5.6.1 and 5.6.2 in the Investigator Brochure (IB) represent the Reference Safety Information to determine expectedness of serious adverse events for expedited reporting. Following the subject's or the legal representative's written consent to participate in the study, all SAEs, whether related or not related to study drug, must be collected, including those thought to be associated with protocol-specified procedures. All SAEs must be collected that occur during the screening period and within 100 days of discontinuation of dosing. If applicable, SAEs must be collected that relate to any later protocol-specified procedure (eg. a follow-up skin biopsy).

The investigator should report any SAE that occurs after these time periods and that is believed to be related to study drug or protocol-specified procedure.

An SAE report should be completed for any event where doubt exists regarding its seriousness.

If the investigator believes that an SAE is not related to study drug, but is potentially related to the conditions of the study (such as withdrawal of previous therapy or a complication of a study procedure), the relationship should be specified in the narrative section of the SAE Report Form.

SAEs, whether related or not related to study drug, and pregnancies must be reported to BMS (or designee) within 24 hours. SAEs must be recorded on the SAE Report Form; pregnancies on a Pregnancy Surveillance Form (electronic or paper forms). The preferred method for SAE data reporting collection is through the eCRF. The paper SAE/pregnancy surveillance forms are only intended as a back-up option when the eCRF system is not functioning. In this case, the paper forms are to be transmitted via email or confirmed facsimile (fax) transmission to:

SAE Email Address: [contact]

SAE [contact]

For studies capturing SAEs/pregnancies through electronic data capture (EDC), electronic submission is the required method for reporting. The paper forms should be used and submitted immediately, only in the event the electronic system is unavailable for transmission. When paper forms are used, the original paper forms are to remain on site.

If only limited information is initially available, follow-up reports are required. (Note: Follow-up SAE reports should include the same investigator term(s) initially reported.)

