10.2 Data Management and Monitoring

Data will be captured in OnCore, Moffitt's Clinical Trials Database. Regulatory documents and case report forms will be monitored internally according to Moffitt Cancer Center Monitoring Policies. Monitoring will be performed regularly to verify data is accurate, complete, and verifiable from source documents; and the conduct of the trial is in compliance with the currently approved protocol/ amendments, Good Clinical Practice (GCP), and applicable regulatory requirements.

To obtain access to OnCore, the site research staff must complete an OnCore Access Request Form and a Moffitt Information Systems Confidentiality Agreement (provided in the MCRN Handbook at the site initiation visit) and submit both to the Coordinating Center. Once the completed forms are received, the site coordinator will receive VPN access, logon/password, and information on how to access OnCore using the VPN. The MCRN Coordinating Center will provide OnCore training to the site once initial access is granted and on an ongoing basis, as needed.

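### Section 6.8.2 gives second malignancies routine CDUS reporting only, while Sections 8.1 and 8.1.1 require any cancer to be handled as an SAE within 24 hours, so new cancers in either arm may go unexpedited and be classified inconsistently

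*Combined protocol and SAP*

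**What the plan says.** Section 6.8 covers radiation therapy adverse events and ends with two short definitions.

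- Section 6.8.1: "A secondary malignancy is a cancer caused by treatment for a previous malignancy". It gives three options for describing the event and no reporting route.
- Section 6.8.2: "A second malignancy is one unrelated to the treatment of a prior malignancy". Its reporting rule follows: "Second malignancies require ONLY routine reporting via CDUS unless otherwise specified".

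The general safety rules are in Section 8.

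- Section 8.1 says that "pregnancy, overdose, cancer, and potential drug induced liver injury (DILI) are not always serious by regulatory definition, these events must be handled as SAEs". It makes no exception for second malignancies.
- Section 8.1.1 sets the timing: "SAEs, whether related or not related to study drug, and pregnancies must be reported to BMS (or designee) within 24 hours".

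The adverse-event rows of the on-treatment and follow-up tables in Section 7.1 refer sites to both places ("See Section 6.8. and Section 8") and do not distinguish the arms. Section 10.2 names the trial's database: "Data will be captured in OnCore". CDUS does not appear in Section 10.2, in Section 8 or in the abbreviation list (Section 12).

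**The concern.** The same event, a new cancer judged unrelated to earlier treatment, carries two incompatible instructions. One limits it to routine reporting through a channel the protocol never sets up. The other requires expedited handling regardless of causality. A site that acts on Section 6.8.2 would not file the 24-hour report, and if the event is also unexpected, the 7- or 15-day report to the FDA described in Section 8.1.1 would not be triggered.

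The statistical stake is the safety comparison. SAE incidence is part of the fourth secondary endpoint (Section 9.2.2), and SAEs are tabulated by treatment group in all treated subjects (Section 9.3.3). If sites resolve the conflict differently, those tables mix two definitions.

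Such events are foreseeable. Section 1.4.1 describes a typically elderly population with disease at sun-exposed sites, and Section 3.2 admits patients with several kinds of prior cancer.

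**Working it through.** The plan states no figure on this point, so the check is mainly a comparison of provisions for one event: a new cancer, unrelated to treatment, arising during treatment or within 100 days of the last dose.

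| Question | Section 6.8.2 | Sections 8.1 and 8.1.1 |
|---|---|---|
| Handling | Routine only | As an SAE |
| Timing | None given | 24 hours |
| Does causality matter? | Yes, it defines the category | No |
| Route | CDUS | eCRF to the funding company; MedWatch to the FDA |

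1. **Do the rules cover the same event?** Yes. Section 8.1 says cancer without qualification, so it includes cancers that meet the Section 6.8.2 definition.

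2. **Is there a stated order of precedence?** Only the closing proviso of Section 6.8.2, which defers to anything specified elsewhere. It cites no section, and the capitalised restriction in the same sentence points the other way. The visit tables name both sections without ranking them.

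3. **Can a site comply with Section 6.8.2?** Not from the protocol. CDUS is neither defined nor set up. That the trial does not use it is an inference from this silence, though a fair one.

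4. **Does causality decide the route?** Under Section 6.8.2 it does. The split from Section 6.8.1 rests on whether treatment caused the cancer, judged in a trial that Section 5 describes as non-blinded. Section 8.1.1 makes SAE reporting independent of that judgment.

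5. **In what period does the conflict operate?** Section 8.1.1 collects all SAEs from screening to 100 days after dosing stops, and later ones only if believed related to study drug or a protocol procedure. A second malignancy is unrelated to treatment by definition, so the conflict lies essentially within that window.

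6. **What is one event worth?** Section 9.1.1 plans 24 patients per arm if both stages are completed. One patient is 1/24 = 0.042, about 4 percentage points of that arm's SAE incidence. For an arm that stops after the first stage of 16, it is 1/16 = 0.0625, about 6 points.

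**The case against.** The best defence is that the proviso in Section 6.8.2 already yields to Section 8.1, which does specify otherwise. Section 8.1.1 adds that an SAE report is due whenever seriousness is in doubt, and a cancer that is life-threatening or leads to inpatient admission is an SAE on the ordinary criteria. A careful site that reads both sections should reach the right answer. All of this stands, and it reduces the likely number of misrouted events. It does not remove an operative sentence that tells the reader the opposite, and a site that takes that sentence at face value may see no doubt to resolve.

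Two stronger readings are tempting, and the documents support neither.

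- **That the problem falls mainly on Arm B.** A reader might infer this because the sentence sits in the radiation section. But a second malignancy is by definition not a treatment effect and can arise in either arm. Radiation-caused cancers belong to Section 6.8.1, which has no CDUS sentence, and the visit tables send both arms to Section 6.8. Uneven application by arm is possible, but nothing in the text shows it.

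- **That events would be lost.** Section 8.2.1 requires every identified nonserious adverse event to go on the CRF until 100 days after the last dose. The Protocol Monitoring Committee meets monthly and reviews all adverse events (Section 8.8). A cancer treated as routine would still be recorded and seen. It would lack expedited reporting and an SAE classification.

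It is also fair to say that this is an inconsistency of wording in safety reporting, not a flaw in the trial's design.

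**Conclusion.** The conflict is real and the sentence is wrong as it stands. The consequence is limited to non-expedited reporting of new cancers and inconsistent SAE classification between sites, in either arm. The primary endpoint, the two-stage rules, the selection of a winner and the sample size are unaffected.

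The number of affected events cannot be estimated: the documents give no rate of new cancers, and any rate brought in from outside would be an assumption. The figure of about 4 percentage points is therefore the weight of one patient in a completed arm of 24, not a predicted bias. It assumes that a cancer handled as an SAE is counted in the SAE tables, and that the patient has no other SAE. If the patient already has one, patient-level SAE incidence does not move, although the reporting failure remains.

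**What to change.** Replace the reporting sentence in Section 6.8.2 with: *Second malignancies, in either arm, are handled and reported as SAEs under Sections 8.1 and 8.1.1.* Delete the reference to CDUS. This applies the protocol's own general SAE rule and keeps its existing collection window.

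A matching pointer in Section 6.8.1 would help readers, since that section gives no reporting route. It is optional, because Section 8.1 already covers all cancers.

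The cost is one sentence in an amendment, a few more SAE forms and possibly a slightly higher reported SAE rate.

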7 STUDY ASSESSMENTS AND PROCEDURES

7.1 Flow Chart/Time and Events Schedule

Table 7.1-1: Screening Procedural Outline

Procedure	Screening Visit (Day -28 till Day -1 prior to Randomization)	Notes
Eligibility Assessments		
Informed Consent	x	
Inclusion/Exclusion Criteria	x	All inclusion/exclusion criteria should be assessed during screening and confirmed prior to randomization.
Medical History	x	
Review of pathology report	x	
Tumor Tissue Samples	x	Sufficient tumor tissue from the resected site of the disease (a block or a minimum of 15 slides) must be available and sent to Moffitt Cancer Center for biomarker analysis. If biopsy is performed at the treatment sites, fresh tumor will be requested to biomarker studies to establish tumor cell lines.
Safety Assessments		
Physical Examination	x	Including height
Vital Signs	x	Including weight, blood pressure (BP), heart rate (HR), temperature
Oxygen saturation	x	By pulse oximetry
Performance Status (ECOG)	x	Within 14 days prior to randomization
Assessment of Signs and Symptoms	x	Within 14 days prior to randomization
Electrocardiogram (ECG)	x	Within 14 days prior to randomization
Laboratory Tests	x	On site/local complete blood count (CBC) w/differential, Chemistry panel including: LDH, AST, ALT, ALP, T.Bili, amylase, lipase, blood urea nitrogen (BUN) or serum urea level, creatinine, uric acid, Ca, Mg, Na, K, Cl, Glucose, endocrine panel (TSH, Free T4, Free T3), Hep B/C (HBV sAG, HCV RNA), within 14 days prior to randomization.
Pregnancy Test	x	WOCBP only (within 24 hours prior to start). Serum or Urine.
Efficacy assessment		
Surveillance assessments	x	Clinical exam and/or CT scan of the involved disease sites and all known sites of resected disease and brain MRI (brain CT allowable if MRI is contraindicated or if there is no known history of resected brain lesions).
Other		
Randomization	x	

Table 7.1-2: On-Treatment Assessments Week 1 - Week 9

Procedure	Wk1	Wk2	Wk3	Wk5	Wk7	Wk9	Notes
Safety Assessments							
Targeted Physical Examination	x	x	x	x	x	x	To be performed within 72 hours of dosing, or while undergoing radiation therapy as an on treatment visit
Vital Signs	x	x	x	x	x	x	Including BP, HR, temperature
Oxygen saturation	x	x	x	x	x	x	By pulse oximetry prior to dosing
Weight and performance status	x	x	x	x	x	x	Within 72 hours of dosing or while undergoing radiation therapy as an on treatment visit
Adverse Events Assessment	Continuously						See Section 6.8. and Section 8
Review of concomitant medications	x	x	x	x	x	x	
Pregnancy Test	x			x		x	Every 4 weeks \pm 1 week. Serum or Urine.
Laboratory Tests	x		x	x	x	x	Within 72 hrs prior to dosing/SBRT to include CBC w/differential, LFT's, BUN or serum urea level, creatinine, Ca, Mg, Na, K, Cl, LDH, Glucose, amylase, lipase, TSH (with reflexive Free T4/T3)
Exploratory Biomarker Assessments							
Plasma	x	x	x		x		Prior to dosing/SBRT
Peripheral Blood Mononuclear Cells (PBMCs)	x	x	x		x		Prior to dosing/SBRT
Efficacy Assessments							
Surveillance Assessments	Every 12 weeks (\pm 7 days) from first dose of study treatment through 12 months (until distant recurrence)						Clinical exam and/or CT scan of the involved disease sites and all known sites of resected disease and brain MRI (brain CT allowable if MRI is contraindicated or if there is no known history of resected brain lesions). Use same imaging method as was used at screening/baseline.
Study Drug							
Randomize	x						
Study Treatment	x	RT	x	x	x	x	First dose to be administered within 14 days of randomization. See Section 5.5.
Outcome Research							
EORTC-QLQ-C30	x				x		Prior to dosing. D1W1 should be completed after randomization but prior to dosing.
EQ5D (optional)	x				x		
WPAI:GH (optional)	x				x		
Health Care Resource Utilization (optional)	x				x		

Table 7.1-3: On-Treatment Assessments Week 11 - Week 21

Procedure	Wk11	Wk13	Wk15	Wk17	Wk19	Wk21	Notes
Safety Assessments							
Targeted Physical Examination	x	x	x	x	x	x	
Vital Signs	x	x	x	x	x	x	Including BP, HR, temperature
Oxygen saturation	x	x	x	x	x	x	By pulse oximetry prior to dosing
Weight and performance status	x	x	x	x	x	x	Within 72 hours of dosing
Adverse Events Assessment	Continuously						See Section 6.8. and Section 8
Review of concomitant medications	x	x	x	x	x	x	
Laboratory Tests	x	x	x	x	x	x	Within 72 hrs prior to dosing to include CBC w/differential, LFT's, BUN or serum urea level, creatinine, Ca, Mg, Na, K, Cl, LDH, Glucose, amylase, lipase, TSH (with reflexive Free T4 and T3)
Pregnancy Test		x		x		x	Every 4 weeks ± 1 week. Serum or Urine.
Exploratory Biomarker							
Plasma		x					Prior to dosing
Peripheral Blood Mononuclear Cells (PBMCs)		x					Prior to dosing
Efficacy Assessments							
Surveillance Assessments	Every 12 weeks (± 7 days) from first dose of study treatment through 12 months (until distant recurrence)						Clinical exam and/or CT scan of the involved disease sites and all known sites of resected disease and brain MRI (brain CT allowable if MRI is contraindicated or if there is no known history of resected brain lesions). Use same imaging method as was used at screening/baseline.
Study Drug							
Study Treatment	x	x	x	x	x	x	See Section 5.5.
Outcome Research							
EORTC-QLQ-C30		x			x		Prior to dosing
EQ5D (optional)		x			x		
WPAI:GH (optional)		x			x		
Health Care Resource Utilization (optional)		x			x		

Table 7.1-4: On-Treatment Assessments Week 23 - Week 33

Procedure	Wk23	Wk25	Wk27	Wk29	Wk31	Wk33	Notes
Safety Assessments							
Targeted Physical Examination	x	x	x	x	x	x	
Vital Signs	x	x	x	x	x	x	Including BP, HR, temperature
Oxygen saturation	x	x	x	x	x	x	By pulse oximetry prior to dosing
Weight and performance status	x	x	x	x	x	x	Within 72 hours of dosing
Adverse Events Assessment	Continuously						See Section 6.8. and Section 8
Review of concomitant medications	x	x	x	x	x	x	
Laboratory Tests	x	x	x	x	x	x	Within 72 hrs prior to dosing to include CBC w/differential, LFT's, BUN or serum urea level, creatinine, Ca, Mg, Na, K, Cl, LDH, Glucose, amylase, lipase, TSH (with reflexive Free T4 and T3)
Pregnancy Test		x		x		x	Every 4 weeks \pm 1 week. Serum or Urine.
Exploratory Biomarker							
Plasma		x					Prior to dosing
Peripheral Blood Mononuclear Cells (PBMCs)		x					Prior to dosing
Tumor Tissue Sample		x					Biopsy at 6 months or at the time of progression
Efficacy Assessments							
Surveillance Assessments	Every 12 weeks (\pm 7 days) from first dose of study treatment through 12 months (until distant recurrence)						Clinical exam and/or CT scan of the involved disease sites and all known sites of resected disease and brain MRI (brain CT allowable if MRI is contraindicated or if there is no known history of resected brain lesions). Use same imaging method as was used at screening/baseline.
Study Drug							
Study Treatment	x	x	x	x	x	x	See Section 5.5.
Outcome Research							
EORTC-QLQ-C30		x			x		Prior to dosing
EQ5D (optional)		x			x		
WPAI:GH (optional)		x			x		
Health Care Resource Utilization (optional)		x			x		

Table 7.1-5: On-Treatment Assessments Week 35 - Week 45

Procedure	Wk35	Wk37	Wk39	Wk41	Wk43	Wk45	Notes
Safety Assessments							
Targeted Physical Examination	x	x	x	x	x	x	
Vital Signs	x	x	x	x	x	x	Including BP, HR, temperature
Oxygen saturation	x	x	x	x	x	x	By pulse oximetry prior to dosing
Weight and performance status	x	x	x	x	x	x	Within 72 hours of dosing
Adverse Events Assessment	Continuously						See Section 6.8. and Section 8
Review of concomitant medications	x	x	x	x	x	x	
Laboratory Tests	x	x	x	x	x	x	Within 72 hrs prior to dosing to include CBC w/differential, LFT's, BUN or serum urea level, creatinine, Ca, Mg, Na, K, Cl, LDH, Glucose, amylase, lipase, TSH (with reflexive Free T4 and T3)
Pregnancy Test		x		x		x	Every 4 weeks ± 1 week. Serum or Urine.
Exploratory Biomarker							
Plasma							Prior to dosing
Peripheral Blood Mononuclear Cells (PBMCs)							Prior to dosing
Efficacy Assessments							
Surveillance Assessments	Every 12 weeks (± 7 days) from first dose of study treatment through 12 months (until distant recurrence)						Clinical exam and/or CT scan of the involved disease sites and all known sites of resected disease and brain MRI (brain CT allowable if MRI is contraindicated or if there is no known history of resected brain lesions). Use same imaging method as was used at screening/baseline.
Study Drug							
Study Treatment	x	x	x	x	x	x	See Section 5.5.
Outcome Research							
EORTC-QLQ-C30		x			x		Prior to dosing
EQ5D (optional)		x			x		
WPAI:GH (optional)		x			x		
Health Care Resource Utilization (optional)		x			x		

Table 7.1-6: On-Treatment Assessments Week 47 - Week 49

Procedure	Wk47	Wk49					Notes
Safety Assessments							
Targeted Physical Examination	x	x					
Vital Signs	x	x					Including BP, HR, temperature
Oxygen saturation	x	x					By pulse oximetry prior to dosing
Weight and performance status	x	x					Within 72 hours of dosing
Adverse Events Assessment	Continuously						See Section 6.8. and Section 8
Review of concomitant medications	x	x					
Laboratory Tests	x	x					Within 72 hrs prior to dosing to include CBC w/differential, LFT's, BUN or serum urea level, creatinine, Ca, Mg, Na, K, Cl, LDH, Glucose, amylase, lipase, TSH (with reflexive Free T4 and T3)
Pregnancy Test		x					Every 4 weeks \pm 1 week. Serum or Urine.
Exploratory Biomarker							
Plasma							Prior to dosing
Peripheral Blood Mononuclear Cells (PBMCs)							Prior to dosing
Efficacy Assessments							
Surveillance Assessments	Every 12 weeks (\pm 7 days) from first dose of study treatment through 12 months (until distant recurrence)						Clinical exam and/or CT scan of the involved disease sites and all known sites of resected disease and brain MRI (brain CT allowable if MRI is contraindicated or if there is no known history of resected brain lesions). Use same imaging method as was used at screening/baseline.
Study Drug							
Study Treatment	x	x					See Section 5.5.
Outcome Research							
EORTC-QLQ-C30		x					Prior to dosing
EQ5D (optional)		x					
WPAI:GH (optional)		x					
Health Care Resource Utilization (optional)		x					

Table 7.1-7: Follow-Up Procedural Outline

Procedure	Follow-up Visits 1 ^a and 2	Survival, Follow up Visits ^b	Notes
Safety Assessments			
Targeted Physical	x		
Adverse Events	x	x	See Section 6.8 . and Section 8
Laboratory Tests	x		
Pregnancy Test	x		Serum or urine
Review of Concomitant Medication	x		
Outcome Research			
EORTC-QLQ-C30	x		
EQ5D	x	x	
WPAI:GH	x		
Health Care Resource	x		
Efficacy Assessments			
Surveillance Assessment	
Every 12 weeks (\pm 7 days) < 12 months
 
Every 12 weeks (\pm 14 days) > 12 months through 24 months
 
Every 6 months (\pm 4 weeks) > 24 months through and up to Year 5
 
Until distant recurrence. All time points are relative to the first dose of study treatment.
		
Clinical exam and/or CT scan of the involved disease sites and all known sites of resected disease and brain MRI (brain CT allowable if MRI is contraindicated or if there is no known history of resected brain lesions). Use same imaging method as was used at screening/baseline.

Survival status			
Survival status	x	x	Every 3 months, maybe accomplished by visit or phone contact, to include subsequent anti-cancer therapy

^a Follow-up visit 1 (FU1) = 30 days (\pm 7 days) from the last dose, Follow-up visit 2 (FU2) = 84 days (\pm 7 days) from follow-up visit 1.

^b First Survival Follow-up visit 30 days (\pm 7 days) after FU2

